#### 3.4 **Reservation and Contact Requirements**

Before enrolling a patient on study, a reservation must be made through the OPEN website and the Study Chair or Vice Chair should be notified. (The patient will need a COG patient ID number in order to obtain a reservation). Patients must be enrolled within 7 calendar days of making a reservation.

Reservations may be obtained 24-hours a day through the OPEN website.

#### 3.5 Informed Consent/Assent

The investigational nature and objectives of the trial, the procedures and treatments involved and their attendant risks and discomforts, and potential alternative therapies will be carefully explained to the patient or the patient's parents or guardian if the patient is a child, and a signed informed consent and assent will be obtained according to institutional guidelines.

#### 3.6 Screening Procedures

Diagnostic or laboratory studies performed exclusively to determine eligibility for this trial must only be done after obtaining written informed consent. This can be accomplished through one of the following mechanisms: a) the COG screening protocol, b) an IRB-approved institutional screening protocol or c) the study-specific protocol. Documentation of the informed consent for screening will be maintained in the patient's research chart. Studies or procedures that were performed for clinical indications (not exclusively to determine eligibility) may be used for baseline values even if the studies were done before informed consent was obtained.

#### 3.7 Eligibility Checklist

NCI Pediatric Early Phase Clinical Trials Network

A program funded by the National Cancer Institute of the National Institutes of Health

Before the patient can be enrolled, the responsible institutional investigator must sign and date the completed eligibility checklist. A signed copy of the checklist will be uploaded into RAVE immediately following enrollment.

#### 3.8 Institutional Pathology Report

Immediately following enrollment, the institutional pathology report for the diagnosis under which the patient is being enrolled must be uploaded into RAVE. The report must include the associated study number and COG patient registration and accession numbers. Personal identifiers, including the patient's name and initials must be removed from the institutional pathology report prior to submission.

#### 3.9 **Study Enrollment**

Patients may be enrolled on the study once all eligibility requirements for the study have been met. Patients who give informed consent for the protocol in order to undergo screening for eligibility are not considered enrolled and should not be enrolled until the screening is completed and they are determined to meet all eligibility criteria. Study enrollment is accomplished by going to the CTSU OPEN (Oncology Patient Enrollment Network) https://open.ctsu.org/open/. For questions, please contact the COG Study Research Coordinator, the **CTSU** helpdesk or OPEN at https://www.ctsu.org/CTSUContact.aspx. Patients must be enrolled before treatment begins. The date protocol therapy is projected to start must be no later than five (5) calendar days after the date of study enrollment. Patients must not receive any protocol therapy prior to enrollment.

#### 3.10 **Dose Assignment**

The dose level will be assigned via OPEN at the time of study enrollment.

#### 4.0 **PATIENT ELIGIBILITY**

All clinical and laboratory studies to determine eligibility must be performed within 7 days prior to enrollment unless otherwise indicated. Laboratory values used to assess eligibility must be no older than seven (7) days at the start of therapy. Laboratory tests need **not** be repeated if therapy starts **within** seven (7) days of obtaining labs to assess eligibility. If a post-enrollment lab value is outside the limits of eligibility, or laboratory values are older than 7 days, then the following laboratory evaluations must be re-checked within 48 hours prior to initiating therapy: CBC with differential, bilirubin, ALT (SGPT), and serum creatinine. If the re-check is outside the limits of eligibility, the patient may not receive protocol therapy and will be considered off protocol therapy. Imaging studies must be obtained within 14 days prior to start of protocol therapy (repeat the tumor imaging if necessary). For patients whose disease is evaluated with a bone marrow examination, the bone marrow aspirates and biopsies are required within 14 days prior to the start of chemotherapy.

Clarification in timing when counting days: As an example, please note that if the patient's last day of prior therapy is September  $1^{st}$ , and the protocol requires waiting at least 7 days for that type of prior therapy, then that patient cannot be enrolled until September  $8^{th}$ .

Important note: The eligibility criteria listed below are interpreted literally and cannot be waived (per COG policy posted 5/11/01). All clinical and laboratory data required for determining eligibility of a patient enrolled on this trial must be available in the patient's

Institute of the Natio

ADVL1515

#### medical or research record which will serve as the source document for verification at the time of audit.

#### 4.1 **Inclusion** Criteria

- 4.1.1 Age: Patients must be > than 12 months and  $\leq 21$  years of age at the time of study enrollment.
- 4.1.2 Diagnosis: Patients with recurrent or refractory solid tumors, including CNS tumors, are eligible. Patients must have had histologic verification of malignancy at original diagnosis or relapse except in patients with intrinsic brain stem tumors, optic pathway gliomas, or in patients with pineal tumors and elevations of CSF or serum tumor markers including alpha-fetoprotein or beta-HCG.
- 4.1.3 Disease Status: Patients must have either measurable or evaluable disease (see Sections 12.2 and 12.3 for definitions).
- 4.1.4 Therapeutic Options: Patient's current disease state must be one for which there is no known curative therapy or therapy proven to prolong survival with an acceptable quality of life.
- Performance Level: Karnofsky  $\geq$  50% for patients > 16 years of age and Lansky  $\geq$ 4.1.5 50 for patients  $\leq$  16 years of age (See Appendix I). Note: Neurologic deficits in patients with CNS tumors must have been relatively stable for at least 7 days prior to study enrollment. Patients who are unable to walk because of paralysis, but who are up in a wheelchair, will be considered ambulatory for the purpose of assessing the performance score.

#### 4.1.6 **Prior** Therapy

- 4.1.6.1 Patients must have fully recovered from the acute toxic effects of all prior anti-cancer therapy and must meet the following minimum duration from prior anti-cancer directed therapy prior to enrollment. If after the required timeframe, the defined eligibility criteria are met, e.g. blood count criteria, the patient is considered to have recovered adequately.
  - a. Cytotoxic chemotherapy or other anti-cancer agents known to be myelosuppressive. See DVL homepage for commercial and Phase 1 investigational agent classifications. For agents not listed, the duration of this interval must be discussed with the Study Chair and the studyassigned Research Coordinator prior to enrollment.
    - $\geq$  21 days after the last dose of cytotoxic or myelosuppressive chemotherapy (42 days if prior nitrosourea).
  - b. Anti-cancer agents not known to be myelosuppressive (e.g. not associated with reduced platelet or ANC counts):  $\geq 7$  days must have elapsed from last dose of agent. See DVL homepage for commercial and Phase 1 investigational agent classifications. For agents not listed,

A program funded by the National Cancer Institute of the National Institutes of Health

THIS PROTOCOL IS FOR RESEARCH PURPOSES ONLY, SEE PAGE 1 FOR USAGE POLICY

the duration of this interval must be discussed with the study chair and the study-assigned Research Coordinator prior to enrollment.

- c. Antibodies:  $\geq 21$  days must have elapsed from infusion of last dose of antibody, and toxicity related to prior antibody therapy must be recovered to Grade  $\leq 1$ .
- d. Corticosteroids: See Section 4.2.2.1. If used to modify immune adverse events related to prior therapy,  $\geq 14$  days must have elapsed since last dose of corticosteroid.
- e. Hematopoietic growth factors: ≥ 14 days must have elapsed since the last dose of a long-acting growth factor (e.g. pegfilgrastim) or 7 days for short-acting growth factor. For agents that have known adverse events occurring beyond 7 days after administration, this period must be extended beyond the time during which adverse events are known to occur. The duration of this interval must be discussed with the Study Chair and the study-assigned Research Coordinator.
- f. Interleukins, Interferons and Cytokines (other than Hematopoietic Growth Factors): ≥ 21 days must have elapsed since the completion of interleukins, interferon or cytokines (other than Hematopoietic Growth Factors).
- g. Stem cell Infusions (with or without TBI):
  - Allogeneic (non-autologous) bone marrow or stem cell transplant, or any stem cell infusion including DLI or boost infusion: ≥ 84 days must have elapsed after infusion, and no evidence of GVHD.
  - Autologous stem cell infusion including boost infusion: ≥42 days must have elapsed after completion.
- h. Cellular Therapy:  $\geq$  42 days must have elapsed since the completion of any type of cellular therapy (e.g. modified T cells, NK cells, dendritic cells, etc.).
- i. XRT/External Beam Irradiation including Protons:  $\geq 14$  days must have elapsed after local XRT;  $\geq 150$  days after TBI, craniospinal XRT or if radiation to  $\geq 50\%$  of the pelvis;  $\geq 42$  days if other substantial BM radiation.
- j. Radiopharmaceutical therapy (e.g., radiolabeled antibody, I-MIBG):  $\geq$  42 days must have elapsed since systemically administered radiopharmaceutical therapy.
- k. Patients must not have received prior exposure to LY2606368.

## 4.1.7 Organ Function Requirements

A program funded by the National Cancer nstitute of the National Institutes of Health This protocol is for research purposes only, see page 1 for usage policy

- 4.1.7.1 Adequate Bone Marrow Function Defined as:
  - a. For patients with solid tumors without known bone marrow involvement:
    - Peripheral absolute neutrophil count (ANC)  $\geq 1000/\text{mm}^3$
    - Platelet count ≥ 75,000/mm^3 (transfusion independent, defined as not receiving platelet transfusions for at least 7 days prior to enrollment)
    - Hemoglobin  $\geq 8.0$  g/dl at baseline (may receive PRBC transfusions)
  - b. Patients with known bone marrow metastatic disease will be eligible for study provided they meet the blood counts in 4.1.7.1.a (may receive transfusions provided they are not known to be refractory to red cell or platelet transfusions). These patients will not be evaluable for hematologic toxicity. At least 5 of every cohort of 6 patients must be evaluable for hematologic toxicity for the dose-escalation part of the study. If dose-limiting hematologic toxicity is observed, all subsequent patients enrolled must be evaluable for hematologic toxicity.

#### 4.1.7.2 Adequate Renal Function Defined as:

- Creatinine clearance or radioisotope GFR  $\ge$  70ml/min/1.73 m^2 or
- A serum creatinine based on age/gender as follows:

Age	Maximum Serum Creatinine (mg/dL)	
	Male	Female
1 to $< 2$ years	0.6	0.6
2 to $< 6$ years	0.8	0.8
6  to < 10  years	1	1
10  to < 13  years	1.2	1.2
13 to < 16 years	1.5	1.4
$\geq$ 16 years	1.7	1.4

The threshold creatinine values in this Table were derived from the Schwartz formula for estimating GFR (Schwartz et al. J. Peds, 106:522, 1985) utilizing child length and stature data published by the CDC.

#### 4.1.7.3 Adequate Liver Function Defined as:

- Bilirubin (sum of conjugated + unconjugated) ≤ 1.5 x upper limit of normal (ULN) for age regardless of baseline.
- SGPT (ALT)  $\leq$  135 U/L (3x ULN). For the purpose of this study, the ULN for SGPT is 45 U/L regardless of baseline.
- Serum albumin  $\geq 2 \text{ g/dL}$ .

#### 4.1.7.4 Adequate Cardiac Function Defined As:

- Shortening fraction of  $\geq 27\%$  by echocardiogram, or
- Ejection fraction of  $\geq$  50% by gated radionuclide study
- $QTc \le 480 \text{ msec}$

institute of the National Institutes of Health

THIS PROTOCOL IS FOR RESEARCH PURPOSES ONLY. SEE PAGE 1 FOR USAGE POLICY

Note: Patients should avoid concomitant medication known or suspected to prolong QTc interval or cause Torsades De Pointes. If possible, alternative agents should be considered.

Patients who are receiving drugs that prolong the QTc are eligible if the drug is necessary and no alternatives are available. See Appendix IV for drugs that may prolong the QTc.

- 4.1.7.5 Adequate Neurologic Function Defined as:
  - Patients with seizure disorder may be enrolled if on anticonvulsants and well controlled.
  - Nervous system disorders (CTCAE v5) resulting from prior therapy must be ≤ Grade 2 with the exception of decreased tendon reflex (DTR). Any grade of decreased tendon reflex is eligible.
  - For patients with CNS tumors, any baseline neurologic deficit, including seizures, must be stable for at least one week prior to initiating study treatment.
- 4.1.8 Informed Consent: All patients and/or their parents or legally authorized representatives must sign a written informed consent. Assent, when appropriate, will be obtained according to institutional guidelines.
- 4.1.9 Tissue blocks or slides must be sent per Section 8.4 if available. If tissue blocks or slides are unavailable, the study chair must be notified prior to study enrollment.

#### 4.2 **Exclusion Criteria**

4.2.1 Pregnancy or Breast-Feeding

Pregnant or breast-feeding women will not be entered on this study because there is yet no available information regarding human fetal or teratogenic toxicities. Pregnancy tests must be obtained in girls who are post-menarchal. Males or females of reproductive potential may not participate unless they have agreed to use an effective contraceptive method both during and for 3 months after participation in this study. Abstinence is an acceptable method of contraception.

- 4.2.2 Concomitant Medications
  - 4.2.2.1 Corticosteroids: Patients receiving corticosteroids must have been on a stable or decreasing dose of corticosteroid for at least 7 days prior to enrollment. If used to modify **immune adverse events** related to prior therapy,  $\geq 14$  days must have elapsed since last dose of corticosteroid (See Section 4.1.6.1.d).
  - 4.2.2.2 Investigational Drugs: Patients who are currently receiving another investigational drug are not eligible.
  - 4.2.2.3 Anti-cancer Agents: Patients who are currently receiving other anti-cancer agents are not eligible.
  - 4.2.2.4 Anti-GVHD agents post-transplant: Patients who are receiving cyclosporine, tacrolimus or other agents to prevent graft-versus-host

disease post bone marrow transplant are not eligible for this trial.

- 4.2.2.5 Strong CYP1A2 Inhibitors: Patients must not have received strong CYP1A2 inhibitors (ciprofloxacin, fluvoxamine, zafirlukast) for at least 7 days prior to enrollment and must not receive them for the duration of the study.
- 4.2.2.6 Infection: Patients who have an uncontrolled infection are not eligible.
- 4.2.2.7 Patients who have received a prior solid organ transplantation are not eligible.
- 4.2.2.8 Patients with a history of allergic reactions attributed to compounds of similar chemical or biologic composition to LY2606368 or to its formulation are not eligible.
- 4.2.2.9 Patients who in the opinion of the investigator may not be able to comply with the safety monitoring requirements of the study are not eligible.

#### 5.0 TREATMENT PROGRAM

#### 5.1 **Overview of Treatment Plan**

Day 1	Day 15	Day 28
LY2606368 IV	LY2606368 IV	End of Cycle/Evaluation

LY2606368 will be administered intravenously over 60 minutes on Days 1 and 15 of a 28 day cycle. A cycle may be repeated for a total of 13 cycles, up to a total duration of therapy of approximately 12 months.

Drug doses should be adjusted based on the BSA calculated from height and weight measured within 7 days prior to the beginning of each cycle.

Criteria for delaying or omitting the Day 15 dose of LY2606368 are specified in Section 6.1.

Patients should be monitored for signs and symptoms of infusion reactions during LY2606368 administration and for 30 minutes after the flush completion. See Section 6.3.4 for management guidelines for infusion reactions.

#### 5.2 Criteria for Starting Subsequent Cycles

A cycle may be repeated every 28 days if the patient has at least stable disease and has again met laboratory parameters as defined in the eligibility section, Section 4.0.

#### 5.3 **Dose Escalation Schema**

5.3.1 Inter-Patient Escalation

institute of the National Institutes of H

The starting dose of LY2606368 will be  $80 \text{ mg/m}^2$  (dose level 1) with dose levels for subsequent groups of patients as follows.

Dose Level	LY2606368 (mg/m²)
0	60
1*	80
2	100
3	125
4	150

\* Starting Dose Level

There will be no escalations beyond dose level 4 ( $150 \text{ mg/m}^2$ ), as previous pediatric Phase 1 studies have rarely defined a MTD greater than 160% of the adult MTD.

If the MTD has been exceeded at the first dose level, then the subsequent cohort of patients will be treated at a dose of  $60 \text{ mg/m}^2$  (dose level 0). If dose level 0 is not well tolerated, further de-escalation will not occur. The study will be closed to accrual.

#### 5.3.2 Intra-Patient Escalation

There will not be intra-patient dose escalation.

#### 5.4 Grading of Adverse Events

Adverse events (toxicities) will be graded according to the NCI Common Terminology Criteria for Adverse Events (CTCAE) version 5.0. All appropriate treatment areas should have access to a copy of the CTCAE version 5.0. A copy of the CTCAE version 5.0 can be downloaded from the CTEP website (http://ctep.cancer.gov). Any suspected or confirmed dose-limiting toxicity should be reported immediately (within 24 hours) to the Study Chair.

#### 5.5 **Definition of Dose-Limiting Toxicity (DLT)**

DLT will be defined as any of the following events that are possibly, probably or definitely attributable to protocol therapy. The DLT observation period for the purposes of dose-escalation will be the first cycle of therapy.

Dose limiting hematological and non-hematological toxicities are defined differently.

#### 5.5.1 Non-hematological dose-limiting toxicity

5.5.1.1 Any Grade 3 or greater non-hematological toxicity attributable to the investigational drug with the specific exclusion of:

- Grade 3 nausea and vomiting < 3 days duration
- Grade 3 liver enzyme elevation, including ALT/AST/GGT, that returns to Grade ≤ 1 or baseline prior to the time for the next treatment cycle. Note: For the purposes of this study the ULN for ALT is defined as 45 U/L and the ULN for AST is defined as 50 U/L. Adverse event grades will be based on increases above the upper limit of normal, regardless of the subject's baseline. See Appendix IX for values that represent thresholds between CTCAE grades.
- Grade 3 fever
- Grade 3 infection

nstitute of the National Institutes of Health

This protocol is for research purposes only, see page 1 for usage policy

- Grade 3 hypophosphatemia, hypokalemia, hypocalcemia or hypomagnesemia responsive to supplementation.
- 5.5.1.2 Non-hematological toxicity that causes a delay of  $\geq$  14 days between treatment cycles.
- 5.5.1.3 Note: Allergic reactions that necessitate discontinuation of study drug will not be considered a dose-limiting toxicity.

#### 5.5.2 Hematological dose limiting toxicity

- 5.5.2.1 In patients evaluable for hematological toxicity (see Section 4.1.7.1), hematological dose limiting toxicity is defined as:
  - Day 15:
    - Grade 4 neutropenia or Grade 3 thrombocytopenia (platelets  $< 50,000/\text{mm}^3$ ) that does not resolve to ANC  $\ge 500/\text{mm}^3$  and platelets  $\ge 50,000/\text{mm}^3$  (transfusion independent) by Day 18 will be considered dose-limiting (See Section 6.1).
  - Grade 4 neutropenia for > 7 days
  - Platelet count < 20,000/mm^3 on 2 separate days, or requiring a platelet transfusion on 2 separate days, within a 7-day period
  - Myelosuppression that causes a delay of > 14 days between treatment cycles.
- 5.5.2.2 Note: Grade 3 or 4 febrile neutropenia will not be considered a doselimiting toxicity.

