# 10.0 CRITERIA FOR REMOVAL FROM PROTOCOL THERAPY AND OFF STUDY CRITERIA

#### 10.1 Criteria for Removal from Protocol Therapy

- a) Clinical (including physical examination or serum tumor markers) or radiographic evidence of progressive disease (See Section 12.0).
- b) Adverse Events requiring removal from protocol therapy (See Section 13.0).
- c) Refusal of protocol therapy by patient/parent/guardian
- d) Non-compliance that in the opinion of the investigator does not allow for ongoing participation.
- e) Completion of 13 cycles of therapy.
- f) Physician determines it is not in the patient's best interest.
- g) Repeated eligibility laboratory studies (CBC with differential, bilirubin, ALT (SGPT) or serum creatinine) are outside the parameters required for eligibility prior to the start of LY2606368 (See Section 8.1).
- h) Study is terminated by Sponsor.
- i) Pregnancy

Patients who are removed from protocol therapy during cycle 1 should continue to have the required observations in Section 8.1 until the originally planned end of the cycle or until all adverse events have resolved per Section 13.4.4, whichever happens LATER. The only exception is with documentation of the patient's withdrawal of consent. Patients who are removed from protocol therapy in subsequent cycles should have the necessary observations to ensure adequate clinical care.

Patients who are off protocol therapy are to be followed until they meet the criteria for Off Study (see below). Ongoing adverse events, or adverse events that emerge after the patient is removed from protocol therapy, but within 30 days of the last dose of investigational agent, must be followed and reported via RAVE and CTEP-AERS (if applicable). Follow-up data will be required unless consent is withdrawn.

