# 11.2 **Definitions**

11.2.1 Evaluable For Adverse Events

Any patient who receives at least one dose of the study drug(s) and/or who experiences a dose-limiting toxicity is considered evaluable for Adverse Events. In addition, for the dose-escalation portion during Cycle 1, patients must receive at least 85% of the prescribed dose per protocol guidelines and must have the appropriate toxicity monitoring studies performed to be considered evaluable for dose limiting toxicity. Patients who do not have DLT and are not considered evaluable for toxicity will be replaced.

- 11.2.2 Maximum Tolerated Dose
  - The MTD will be the maximum dose at which fewer than one-third of patients experience DLT (See Section 5.5) during Cycle 1 of therapy.

PAGE 1 FOR USAGE POLICY

ADVL1515

- In the unlikely event that two DLTs observed out of 6 evaluable patients are different classes of Adverse Effects (e.g. hepatotoxicity and myelosuppression), AND all of the following conditions are met, expansion of the cohort to 12 patients will be considered:
  - One of the DLTs does not appear to be dose-related
  - The Adverse Effects are readily reversible
  - The study chair, DVL statistician, DVL committee chair or vice chair, and IND sponsor all agree that expansion of the cohort is acceptable

If fewer than 1/3 of patients in the expanded cohort experience dose-limiting toxicities, the dose escalation can proceed.

• The DLTs observed in the pharmacokinetic (PK) expansion cohort will be counted towards the total number of DLTs observed at the MTD during the dose escalation portion of the study. If  $\geq 1/3$  of the cohort of patients at the MTD (during the dose escalation plus the PK expansion) experience DLT then the MTD will be exceeded.

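### Two DLT criteria can be met only by delaying a next cycle, so a patient who leaves therapy at the end of Cycle 1 cannot be scored on them, yet stays evaluable as without DLT

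*Combined protocol and SAP*

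**What the plan says.** **The two criteria.** Section 5.5.2.1 ends its list of hematological DLTs with "Myelosuppression that causes a delay of > 14 days between treatment cycles". Section 5.5.1.2 has "Non-hematological toxicity that causes a delay of" 14 days or more between cycles. Neither has wording for a patient who gets no further cycle.

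**Who gets a next cycle.** Section 5.2: "A cycle may be repeated every 28 days if the patient has at least stable disease", with laboratory values again meeting the eligibility limits. The Section 8.1 table schedules a tumor evaluation at the end of Cycle 1. Section 10.1 removes a patient from therapy for "Clinical (including physical examination or serum tumor markers) or radiographic evidence of progressive disease"; refusal and physician judgment are also grounds.

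**Who is evaluable.** For Cycle 1 of dose escalation, Section 11.2.1 says "patients must receive at least 85% of the prescribed dose per protocol guidelines" and must have the monitoring done. It requires neither recovery nor a second cycle. On replacement it says: "Patients who do not have DLT and are not considered evaluable for toxicity will be replaced".

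**The window.** Section 5.5: "The DLT observation period for the purposes of dose-escalation will be the first cycle of therapy". Section 11.2.2 likewise defines the MTD by DLT in Cycle 1.

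**Follow-up.** Under Section 10.1, patients removed during Cycle 1 stay under observation "until the originally planned end of the cycle or until all adverse events have resolved", whichever is later. For removals in later cycles it asks only for the observations that clinical care needs. Adverse events ongoing or emerging within 30 days of the last dose must be followed and reported in either case. Section 10.2 takes patients off study 30 days after the last dose, or sooner, for example on enrollment in another COG therapeutic study.

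**The concern.** Take two patients in one cohort, each with a platelet count of 60,000/mm³ from Day 28 to Day 45 and no other DLT. One has stable disease: Cycle 2 is held for more than 14 days and the patient is a DLT. The other has progressed on the end-of-Cycle-1 scan: there is no Cycle 2, so no delay and no DLT. The second patient is not replaced either.

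Whether this toxicity counts therefore depends on tumor outcome or on a decision to stop. The error can only remove DLTs, never add them. DLT counts drive every escalation decision in Section 11.3, and Section 11.2.2 adds DLTs from the PK expansion to the count at the MTD. Myelosuppression is one of the expected dose-limiting toxicities (Section 2.2.2).

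**Working it through.** No sample size or other stated figure depends on this definition, so there is none to reproduce. The check is textual, followed by an illustration.

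**1. Which toxicity is lost.** Restart needs ANC of at least 1000 and platelets of at least 75,000 (Sections 4.1.7.1 and 5.2). A patient with no next cycle still has a DLT for:
- Grade 4 neutropenia lasting more than 7 days
- platelets below 20,000, or transfusion, on 2 days within 7
- failure of the Day 15/18 rule
- non-excluded Grade 3 or higher non-hematological toxicity.

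The Grade 3 liver-enzyme exclusion is judged at the time the next cycle is due, so it needs no actual delay. What escapes is:
- persistent ANC 500-999
- persistent platelets 50,000-74,999
- lower platelet counts that arise after the Day 15/18 check and miss the below-20,000 and transfusion criteria
- persistent lower-grade non-hematological toxicity. For example, ALT of 136-225 U/L is Grade 2 in Appendix IX but above the 135 U/L limit in Section 4.1.7.3.

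**2. Timing.**
- Planned Cycle 2 start: Day 28 + 1 = Day 29.
- 14-day point: 29 + 14 = Day 43. The hematological criterion (more than 14 days) is met from Day 44.
- Off study after a Day 15 dose: 15 + 30 = Day 45.

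The information would normally fall inside planned follow-up. It also falls after the 28-day cycle, so the documents must say whether it counts for escalation.

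**3. Size, under assumptions.** Let p be the true DLT rate, f the share of true DLTs that meet only a delay criterion, and q the share of evaluable patients who leave at the end of Cycle 1. The documents give neither f nor q; I assume f of 10-50% and q of 20-60%, with leaving independent of toxicity.

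Scored rate: p' = p × (1 − f × q)

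Chance of 0-1 DLT in six: (1 − p')⁶ + 6p'(1 − p')⁵

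Section 11.2.2 requires a rate below one-third, so p = 1/3 is the first rate that it does not accept. With all DLTs scored, the chance is 256/729 = 0.351. With losses:

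| f | q = 20% | q = 40% | q = 60% |
|---|---|---|---|
| 10% | 0.364 | 0.378 | 0.392 |
| 30% | 0.392 | 0.435 | 0.480 |
| 50% | 0.420 | 0.495 | 0.574 |

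Example, f = 50% and q = 60%: p' = 0.333 × (1 − 0.30) = 0.233, giving 0.574.

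If only 2 percentage points of the one-third are delay-only (f = 0.02/0.333 = 6%), the chance is 0.359 at q = 20% and 0.375 at q = 60%.

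Over the same f and q grid, a true rate of 0.40 gives 0.233 rising to 0.246-0.464. A true rate of 0.25 gives 0.534 rising to 0.546-0.717.

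This is a binomial for a full cohort of six, not a simulation of the rolling-six rules.

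**The case against.** **The window may remove the asymmetry.** If only events completed within Cycle 1 count, a delay that reaches 14 days on Day 43 counts for nobody, and both patients are scored alike. This stands as a condition on the harm. But the two criteria would then do nothing in escalation, so the text needs repair on either reading.

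**Delay-only DLTs may be rare.** Section 2.3.1 reports an adult neutrophil nadir on Day 8, Grade 4 neutropenia lasting under 5 days, and Grade 4 thrombocytopenia in 6% at 105 mg/m². A delay-only event needs toxicity to last about 28 days after a Day 15 dose and to miss every other criterion. This stands: the effect may be only 1 to 2 points.

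**Readings that go too far.**
- A reader might infer that any prolonged platelet count of 20,000-75,000 is missed in a progressing patient. The Day 15/18 and transfusion criteria catch part of that range.
- A reader might infer that such a patient can never meet a delay criterion. One whose Cycle 2 had already been held long enough before progression could.
- A reader might count all early leavers. Those who leave before the Day 15 dose without DLT would generally fall below 85% of dose and be replaced.
- A reader might work at a true rate of 25% and treat the rise above 53.4% as unsafe doses passing. Section 11.2.2 accepts a 25% dose.

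**Scoring as without DLT is inferred.** It follows from Sections 11.2.1 and 11.3 but is not stated. The study chair's DLT evaluations are reviewed weekly (Section 14.3.2). That review could notice a case, but no rule tells it how to score one.

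**Conclusion.** The gap is real on the plan's wording. The same unresolved toxicity is a DLT in a patient who stays on study and not in an evaluable patient who leaves at the end of Cycle 1, and the bias is always towards under-counting. It is confined to toxicity that meets no other criterion, and it affects escalation only if the delay criteria count despite the Cycle 1 window.

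Its size cannot be settled from the documents. At a true rate of one-third, the chance that a cohort of six shows 0-1 DLT rises from 35% to about 36% if delay-only DLTs are rare. It reaches 57% if half of DLTs are delay-only and 60% of patients leave. All of this rests on assumed f and q, and on leaving being independent of toxicity. The documents do not support a claim that the MTD will be materially too high. They do support correcting the definition, because it feeds a primary aim and the correction is small.

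**What to change.** 1. Keep the existing day limits. Word Sections 5.5.1.2 and 5.5.2.1 (last bullet) as attributable toxicity that has not recovered to the criteria for starting the next cycle by that many days after its planned start, whether or not another cycle is given. Sections 6.2.5 and 6.3.3 already count from the planned start, for removal from therapy.
2. State that these criteria count for dose escalation, and reconcile this with the Cycle 1 window in Sections 5.5 and 11.2.2.
3. Reconcile the two limits, which read 14 days or more in one criterion and more than 14 days in the other.
4. Score patients who leave after Cycle 1 from the 30-day adverse-event follow-up in Sections 10.1 and 10.2.
5. In Section 11.2.1, keep patients who have already recovered as evaluable, with no further follow-up. Treat as inevaluable only a patient with documented unresolved attributable toxicity, no DLT, and follow-up cut short before the limit, for example by other anticancer therapy.

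**Cost.** Wording changes, one or two extra laboratory checks, and a later escalation decision for the few patients who leave with unresolved toxicity. A broader rule, making everyone not followed to Day 43-44 inevaluable, would not be cheap. It would replace recovered patients, and with 20-60% leaving it could exceed the 20% inevaluable allowance in Section 11.1.
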